4.6 Efficacy Assessments

4.6.1 Baseline Assessments

Baseline assessments should be performed within 28 days prior to the initiation of study utilizing CT or MRI. In addition to chest, abdomen, pelvis, and brain, all known sites of disease should be assessed at baseline.

4.6.2 Response Criteria

Subjects will be evaluated for tumor response beginning 6 weeks *from treatment and continuing every 6 weeks (± 1 wk) for the first 13 months from treatment and every 12 weeks (± 1 wk) thereafter*, until disease progression is documented or treatment is discontinued (whichever occurs later).

4.6.3 Therapeutic Response

Tumor assessments for ongoing study treatment decisions will be completed by the investigator using RECIST (Response Evaluation Criteria in Solid Tumors) 1.1 criteria. Traditional measures of response reflect when a treatment is working and measures of progression indicate when a drug should be stopped.

Measurable disease

STU072016-044, [name], FormA-ResearchProtocol-V7.0-09.30.19, Mod_14, 10-23-19 (2)

Page 55 of 99 (BMS CA209-444) V. V6.0 date March 1, 2019

This material is the property of the [UTSW Simmons Cancer Center](#). Do not disclose or use except as authorized in writing by the study sponsor.

Following RECIST 1.1, tumor lesions must be accurately measured in at least one dimension (longest diameter in the plane of measurement is to be recorded) with a minimum size of:

- 10 mm by CT scan (CT scan slice thickness no greater than 5 mm)
- 10 mm caliper measurement by clinical exam (lesions which cannot be accurately measured with calipers should be recorded as non-measurable)
- 20 mm by chest x-ray

Malignant lymph nodes: To be considered pathologically enlarged and measurable, a lymph node must be ≥ 15 mm in short axis when assessed by CT scan (CT scan slice thickness recommended to be no greater than 5 mm).

Nonmeasurable disease

Following RECIST 1.1, all other lesions (or sites of disease) will be considered nonmeasurable disease. This includes small lesions (longest diameter < 20 mm with conventional techniques or < 10 mm using spiral CT scan) and any of the following:

- bone lesions
- ascites
- pleural or pericardial effusion
- lymphangitis cutis or pulmonis
- abdominal masses that are not confirmed and followed by imaging techniques
- cystic lesions
- lesions occurring within a previously irradiated area unless they are documented as new lesions since the completion of radiation therapy

4.6.4 Evaluation of Target lesions

Following RECIST 1.1, progression in a nodal or visceral site (ie, liver and lung) is sufficient to document disease progression. The presence or absence of nodal and visceral disease before and after treatment should be recorded separately.

All measurable lesions (up to a maximum of 5 lesions per organ and 10 lesions in total) will be identified as target lesions to be measured and recorded at baseline. The target lesions should be representative of all involved organs. Target lesions will be selected

on the basis of size (ie, the largest area) and suitability for accurate, repeated measurements (either by imaging techniques or clinically). The sum of the longest diameter (LD) of all target lesions will be calculated and reported as the baseline sum LD. The baseline sum LD will be used as a reference by which to characterize the objective tumor response.

Because small lymph nodes are difficult to measure accurately and may not be malignant, the greatest diameter of a lymph node must measure at least 1.5 cm by spiral CT to be considered a target lesions.

Table 7. RECIST response criteria for target lesions

Response	Evaluation of Soft-Tissue Lesions
Complete response (CR)	The disappearance of clinical and radiological evidence of all target lesions and normalization of tumor marker levels
Partial response (PR)	A decrease from baseline $\geq 30\%$ in the sum of the LD of all target lesions
Progressive disease (PD)	An increase $\geq 20\%$ in the sum of the LD of all target lesions based on the smallest sum LD since treatment started or the appearance of one or more new lesions or the appearance of new lesions
Stable disease (SD)	Neither sufficient shrinkage to qualify for PR nor sufficient increase to qualify for PD based on the smallest sum LD recorded since treatment started

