2.3 Study Population

For entry into the study, the following criteria MUST be met.

2.3...1 Inclusion Criteria

Eligibility waivers are not permitted. Subjects must meet all of the inclusion and exclusion criteria to be registered to the study. Study treatment may not begin until a subject is registered

1) *Signed Written Informed Consent*

- Willing and able to provide informed consent

2) *Target Population*

- Histological confirmation of RCC with a clear-cell component
- Metastatic (AJCC Stage IV) RCC
- Prior adjuvant or neoadjuvant therapy for localized or locally advanced RCC is allowed provided recurrence occurred = or > 6 months after the last dose of the adjuvant or neoadjuvant therapy
- Any number of prior systemic treatment regimen in the advanced/metastatic setting is allowed (cytokine, anti-angiogenic, mTOR inhibitor or clinical trial) including previously untreated patients
- Karnofsky Performance Status (KPS) of at least 70%
- Life expectancy of at least 3 months
- At least 2 metastatic sites of which at least 1 must be measurable as per RECIST 1.1

- Archival Formalin-fixed paraffin-embedded (FFPE) tumor tissue must be available for correlative studies (Note: Fine Needle Aspiration [FNA] and bone metastases samples are not acceptable for submission)
- Patients with favorable, intermediate and poor risk categories will be eligible for the study. *Patients must be categorized according to favorable versus intermediate/poor risk status at registration. International Metastatic RCC Database Consortium (IMDC) must be used to determine prognostic factors (Appendix 1)*

2.3.2 Exclusion Criteria:

1) Target Disease Exceptions

- Subjects with previously treated brain or CNS metastases are eligible provided that the subject has recovered from any acute effects of radiotherapy and is not requiring steroids, and any whole brain radiation therapy was completed at least 4 weeks prior to study drug administration, or any stereotactic radiosurgery was completed at least 2 weeks prior to study drug administration. Liver metastases will not be included as part of the radiated lesions to be treated.

2) Medical History and Concurrent Diseases

- Prior treatment with an anti-PD-1, anti-PD-L1, anti-PD-L2, anti-CD137, or anti-CTLA-4 antibody, or any other antibody or drug specifically targeting T-cell co-stimulation or checkpoint pathways. Prior treatment with HD IL-2 is allowed.

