small (eg, 2 mm). However, sometimes lesions or lymph nodes which are recorded as target lesions at baseline become so faint on CT scan that the radiologist may not feel comfortable assigning an exact measure and may report them as being 'too small to measure'. When this occurs it is important that a value be recorded on the case report form. If it is the opinion of the radiologist that the lesion has likely disappeared, the measurement should be recorded as 0 mm. If the lesion is believed to be present and is faintly seen but too small to measure, a default value of 5 mm should be assigned (Note: It is less likely that this rule will be used for lymph nodes since they usually have a definable size when normal and are frequently surrounded by fat such as in the retroperitoneum; however, if a lymph node is believed to be present and is faintly seen but too small to measure, a default value of 5 mm should be assigned in this circumstance as well). This default value is derived from the 5 mm CT slice thickness (but should not be changed with varying CT slice thickness). The measurement of these lesions is potentially non-reproducible, therefore providing this default value will prevent false responses or progressions based upon measurement error. To reiterate, however, if the radiologist is able to provide an actual measure, that should be recorded, even if it is below 5 mm.

Lesions that split or coalesce on treatment

When non-nodal lesions 'fragment', the longest diameters of the fragmented portions should be added together to calculate the target lesion sum. Similarly, as lesions coalesce, a plane between them may be maintained that would aid in obtaining maximal diameter measurements of each individual lesion. If the lesions have truly coalesced such that they are no longer separable, the vector of the longest diameter in this instance should be the maximal longest diameter for the 'coalesced lesion'.

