4.6.9 Evaluating best overall response

The best overall response is the best response recorded from the start of treatment until either disease progression or recurrence. The investigator's determination of best overall response will be based both on response criteria and on confirmation criteria. To be assigned a status of partial response or complete response, changes in tumor measurements must be confirmed by repeat assessment performed at least 6 weeks after the criteria for response are first met. To confirm stable disease, follow-up measurements must meet SD criteria at a minimum interval of 6 weeks after SD was first documented. Table 9 can be used as an assessment tool.

Table 9. Assessing Overall Response

Target Lesions	Non-target Lesions	New Lesions	Overall Response
CR	CR	No	CR
CR	Incomplete response/SD	No	PR
PR	Non-PD	No	PR
SD	Non-PD	No	SD
PD	Any	Yes or No	PD
Any	PD	Yes or No	PD
Any	Any	Yes	PD

Abbreviations: CR, complete response; PD, progressive disease; PR, partial response; SD, stable disease.

STU072016-044, [name], FormA-ResearchProtocol-V7.0-09.30.19, Mod_14, 10-23-19 (2)

Page 60 of 99 (BMS CA209-444) V. V6.0 date March 1, 2019

This material is the property of the [UTSW Simmons Cancer Center](#). Do not disclose or use except as authorized in writing by the study sponsor.

Patients with global deterioration of health status who require treatment to be discontinued without objective evidence of disease progression should be classified as having symptomatic deterioration. Every effort should be made to document their objective progression, even after discontinuing treatment.

Patients who do not have tumor response assessment due to rapid progression or toxicity will be considered non-responders, will be included in the denominator for the response rate, and will be classified into one of the categories listed below:

- death attributed to disease progression
- early discontinuation attributed to disease progression
- death attributed to drug toxicity
- early discontinuation attributed to drug toxicity

Note: If a patient receives subsequent therapy before tumor progression is documented, the reason for changing therapy must be reported. Reasons include clinical progression, drug toxicity, or secondary therapy for maintaining tumor response.

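### Table 7 declares progression on a 20% relative rise with no minimum increase in millimetres, so measurement error alone can produce progression when the smallest target sum is below 25 mm

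*Combined protocol and SAP*

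**What the plan says.** Section 4.6.3 has investigators assess tumours "using RECIST (Response Evaluation Criteria in Solid Tumors) 1.1 criteria". Section 4.6.4 then prints the working definitions in Table 7. Partial response is a fall of at least 30% from baseline "in the sum of the LD of all target lesions". Progression is a rise of at least 20% "in the sum of the LD of all target lesions based on the smallest sum LD since treatment started", or a new lesion. Neither section gives a minimum rise in millimetres.

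Section 4.6.5 keeps very small readings in the sum, with 2 mm as its example. For a lesion seen faintly but too small to measure, "a default value of 5 mm should be assigned"; a lesion judged to have disappeared is recorded as 0 mm. The section concedes that such readings may not be reproducible, and says that "providing this default value will prevent false responses or progressions based upon measurement error".

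Table 9 turns target progression into overall progression. Section 4.6.9 takes best response only up to progression, and requires that "changes in tumor measurements must be confirmed by repeat assessment performed at least 6 weeks after the criteria for response are first met". Section 4.6.10 asks for progression to be verified where it is equivocal, and withdraws it if repeat scans do not confirm it. The synopsis ends TTP and DOR at progression; PFS is listed without a definition.

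**The concern.** A purely relative threshold shrinks with the tumour. The deeper the response, the fewer millimetres separate a stable patient from a progression call, and section 4.6.5 identifies that size range as the one where readings are least reliable. The plan therefore sets out to prevent false progression from measurement error in one section and leaves the route open in the section before it.

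Two things are at stake. At the confirmation scan, a false progression closes the best-response window before the response is confirmed, so a true responder drops out of the primary ORR. Later in follow-up, a false progression ends TTP, DOR and PFS too early, and does so in patients with the smallest residual disease.

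Small sums are possible under the entry criteria. Section 2.3 asks for "At least 2 metastatic sites of which at least 1 must be measurable as per RECIST 1.1", and section 4.6.3 accepts a lesion of 10 mm on CT as measurable.

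**Working it through.** **The plan's own figure.** Section 4.6.7 equates a 20% rise in diameter with a 73% rise in volume. 1.2³ − 1 = 0.728, so this reproduces.

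**Trigger in millimetres** = 0.20 × nadir sum.

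| Nadir sum (mm) | Rise that counts as progression (mm) |
|---|---|
| 5 | 1 |
| 10 | 2 |
| 15 | 3 |
| 20 | 4 |
| 25 | 5 |
| 50 | 10 |

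A 5 mm minimum would change the rule only below 25 mm, since 5 / 0.20 = 25.

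**Example.** Baseline 20 mm, week 6 reading 8 mm, week 12 reading 10 mm.
- Week 6 against baseline: (8 − 20)/20 = −60%, partial response.
- Week 12 against baseline: (10 − 20)/20 = −50%, still response-sized.
- Week 12 against nadir: (10 − 8)/8 = +25%, progression by Table 7 and so overall progression by Table 9.

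**Jumps from the recording rules alone.** A lesion read as 2 mm and then given the 5 mm default adds 3 mm, which is progression at any nadir sum up to 3/0.20 = 15 mm. A lesion recorded as 0 mm and then as 5 mm adds 5 mm, which is progression up to 5/0.20 = 25 mm.

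**Chance of false progression in a stable patient.** The documents give no measurement SD, so I assume 0.5 to 2 mm for the sum. Each reading is the true residual plus normal error, rounded to 1 mm. Progression is a rise of at least 20% over the running minimum, with or without a rise of at least 5 mm. No verification rescan is applied. At the confirmation scan:

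| SD (mm) | 10 mm residual, as written | 10 mm, with 5 mm minimum | 15 mm residual, as written | 15 mm, with 5 mm minimum |
|---|---|---|---|---|
| 0.5 | 2.7% | 0% | 0.04% | 0% |
| 1 | 14.8% | 0.1% | 4.2% | 0.1% |
| 1.5 | about 23% | 1.8% | about 12% | 1.7% |
| 2 | about 28% | 5.7% | about 18% | 5.7% |

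A hand check without rounding: for two readings of a stable sum T with SD s, the chance that the second is at least 1.2 times the first is the upper normal tail at 0.20T / (s√(1 + 1.2²)). With T = 10 and s = 1 this is 2/1.562 = 1.28, or 10.0%. Rounding to whole millimetres, also an assumption, raises it to 14.8%.

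**Over 8 scans** (8 × 6 = 48 weeks). At SD 1 mm, the rule as written gives 87% at 10 mm and about 47% at 15 mm, against 2% with the minimum. At SD 2 mm it gives about 98.6% and 93%, against 58%. With the minimum, the figures at SD 0.5, 1, 1.5 and 2 mm are about 0%, 2%, 27% and 58%.

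**Effect of section 4.6.10.** If every progression call had one rescan, the confirmation-scan rate at SD 1 mm would fall from 14.8% to about 6% at 10 mm, and from 4.2% to 1.0% at 15 mm. A residual risk stays because the rescan is compared with the same nadir. If the true size is 10 mm and the nadir was read as 8 mm, a rescan at the true 10 mm is still +25% and confirms the error.

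**The case against.** Four objections carry weight.

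- **There is a safeguard.** Section 4.6.10 makes an equivocal progression reversible, and a patient still 50% below baseline is an obvious candidate. This stands as mitigation. However, the section does not define equivocal, does not require a rescan when the printed 20% rule is met, and cannot correct a nadir read too low.
- **RECIST 1.1 is the named standard.** Table 7 may simply be an incomplete transcription. That is a reason to reconcile the two, because the table is the only operative rule the plan prints.
- **The scope is narrow.** Section 4.6.4 puts up to 10 target lesions in the sum, so a residual below 25 mm means low target burden or deep regression. This stands, and the documents do not say how many patients that covers. Once a response is confirmed, later false progression cannot remove it from ORR; the 8-scan figures bear on the secondary, descriptive endpoints.
- **The 5 mm figure is borrowed.** In section 4.6.5 it is a lesion size, not a minimum change. It is a reasonable anchor, not a value the plan prescribes for this purpose.

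Two stronger readings are tempting. A reader might infer that measuring from the smallest sum since treatment started leaves out baseline, so that target growth could never be progression at week 6. The documents do not support this: section 4.6.4 makes the baseline sum a reference for response, new lesions and non-target progression count at any scan, and no assessor would apply the phrase that way. The progressive-disease count in Table 1 covers progression as best response by any route at any time, so it does not measure such an effect. A reader might also infer that the ORR verdict will be wrong. One response is 1/25 = 4 percentage points, so a lost response could matter near the cut-off, but no expected number of lost responses can be derived.

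**Conclusion.** The point holds in limited form. As printed, Table 7 lets a rise of about 1 to 5 mm count as progression whenever the nadir sum is between 5 and 25 mm, in a size range where the plan itself doubts the readings. This can block confirmation of a response and create early TTP, DOR and PFS events.

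The size depends on the assumed SD, on rounding to 1 mm and on no rescan being done. For a stable 10 mm residual, the confirmation-scan risk runs from 2.7% to about 28% over SDs of 0.5 to 2 mm; for 15 mm, from 0.04% to about 18%. Verification under section 4.6.10 would lower these figures by an amount that depends on how often it is used. Above 25 mm, a 5 mm minimum would change nothing. The number of patients affected cannot be stated. The change is worth making because it is cheap and protects the primary endpoint, not because a large bias has been shown.

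**What to change.** In the Table 7 progression cell, require a rise of at least 20% **and** at least 5 mm over the smallest sum on study, or a new lesion. The 5 mm matches the slice thickness in section 4.5.1 and the default value in section 4.6.5. Reconcile Table 7 with the RECIST 1.1 standard named in section 4.6.3, so that one rule governs. Two optional clarifications: say that the baseline sum is included in the reference, here and in the stable-disease row, and say what counts as equivocal in section 4.6.10.

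This concerns how the endpoints are derived. How it bears on treatment decisions under sections 2.8 and 3.5 is for the investigators.

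The cost is one table cell and the response-derivation program, with no new scans. The downside is that true growth of less than 5 mm in a small residual is called about one scan later. The minimum reduces the problem without eliminating it: false progression over 8 scans is still about 27% at SD 1.5 mm and 58% at SD 2 mm, and a 0 mm to 5 mm recording jump still just meets the threshold.

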4.6.5 Special Notes on the Assessment of Target Lesions

Lymph nodes

Lymph nodes identified as target lesions should always have the actual short axis measurement recorded (measured in the same anatomical plane as the baseline examination), even if the nodes regress to below 10 mm on study. This means that when lymph nodes are included as target lesions, the 'sum' of lesions may not be zero even if complete response criteria are met, since a normal lymph node is defined as having a short axis of < 10 mm. Case report forms or other data collection methods may therefore be designed to have target nodal lesions recorded in a separate section where, in order to qualify for CR, each node must achieve a short axis < 10 mm. For PR, SD and PD, the actual short axis measurement of the nodes is to be included in the sum of target lesions.

Target lesions that become 'too small to measure'

While on study, all lesions (nodal and non-nodal) recorded at baseline should have their actual measurements recorded at each subsequent evaluation, even when very

STU072016-044, [name], FormA-ResearchProtocol-V7.0-09.30.19, Mod_14, 10-23-19 (2)

Page 57 of 99 (BMS CA209-444) V. V6.0 date March 1, 2019

This material is the property of the [UTSW Simmons Cancer Center](#). Do not disclose or use except as authorized in writing by the study sponsor.

small (eg, 2 mm). However, sometimes lesions or lymph nodes which are recorded as target lesions at baseline become so faint on CT scan that the radiologist may not feel comfortable assigning an exact measure and may report them as being 'too small to measure'. When this occurs it is important that a value be recorded on the case report form. If it is the opinion of the radiologist that the lesion has likely disappeared, the measurement should be recorded as 0 mm. If the lesion is believed to be present and is faintly seen but too small to measure, a default value of 5 mm should be assigned (Note: It is less likely that this rule will be used for lymph nodes since they usually have a definable size when normal and are frequently surrounded by fat such as in the retroperitoneum; however, if a lymph node is believed to be present and is faintly seen but too small to measure, a default value of 5 mm should be assigned in this circumstance as well). This default value is derived from the 5 mm CT slice thickness (but should not be changed with varying CT slice thickness). The measurement of these lesions is potentially non-reproducible, therefore providing this default value will prevent false responses or progressions based upon measurement error. To reiterate, however, if the radiologist is able to provide an actual measure, that should be recorded, even if it is below 5 mm.

Lesions that split or coalesce on treatment

When non-nodal lesions 'fragment', the longest diameters of the fragmented portions should be added together to calculate the target lesion sum. Similarly, as lesions coalesce, a plane between them may be maintained that would aid in obtaining maximal diameter measurements of each individual lesion. If the lesions have truly coalesced such that they are no longer separable, the vector of the longest diameter in this instance should be the maximal longest diameter for the 'coalesced lesion'.

4.6.6 Evaluation of Non-Target Lesions

This section provides the definitions of the criteria used to determine the tumor response for the group of non-target lesions. While some non-target lesions may actually be measurable, they need not be measured and instead should be assessed only qualitatively at the time points specified in the protocol.

Table 8. RECIST response criteria for non-target lesions

STU072016-044, [name], FormA-ResearchProtocol-V7.0-09.30.19, Mod_14, 10-23-19 (2)

Page 58 of 99 (BMS CA209-444) V. V6.0 date March 1, 2019

This material is the property of the [UTSW Simmons Cancer Center](#). Do not disclose or use except as authorized in writing by the study sponsor.

Response	Evaluation of Soft-Tissue Lesions
Complete response (CR)	Disappearance of all non-target lesions and normalization of tumor marker level. All lymph nodes must be non-pathological in size (< 10mm short axis)
Non-CR/Non-PD	Persistence of one or more non-target lesion(s) and/or maintenance of tumor marker level above the normal limits
Progressive disease (PD)	Unequivocal progression (see comments below) of existing non-target lesions. (Note: the appearance of one or more new lesions is also considered progression)

